### 6.1.4 Treatment duration

The planned treatment duration is three months.

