2.1.1.5 On-treatment period

The on-treatment period lasts from the date of first administration of study treatment to 30 days after the date of the last actual administration of any study treatment, i.e., date of the last actual administration of any study treatment (from 'Study treatment' CRF) – date of first administration of study treatment (from 'Study treatment' CRF) +1 + 30.

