2.8.1 Adverse events (AEs)

Summary tables for AEs and SAEs will summarize only on-treatment events, with a start date during the on-treatment period (TEAEs and TESAEs, respectively). The on-treatment period lasts from the date of first administration of study treatment to 30 days after the date of the last actual administration of any study treatment ([Section 2.1.1.5](#)).

The secondary endpoint for safety is the frequency of TEAEs and TESAEs in all subjects.

The number (and proportion) of subjects with TEAE will be summarized for ocular and non-ocular AEs separately, by treatment group and overall in the following ways:

- Overall summary of subjects with any TEAE, any severe TEAE, any study drug related TEAE, any TEAE leading to study drug discontinuation, any TESAE, any study drug related TESAE
- TEAE by primary system organ class and preferred term
- TEAE by primary system organ class, preferred term and maximum severity
- TESAE by primary system organ class and preferred term
- Study drug related TESAE by system organ class and preferred term
- TEAE leading to study drug discontinuation by primary system organ class and preferred term
- TEAE leading to study drug interruption by primary system organ class and preferred term

Except for the first table, all the above AE summaries will be provided by descending frequency in the UNR844-CI group. A subject with multiple adverse events within a primary system organ class is only counted once towards the total of the primary system organ class.

Any other AEs or SAEs will be listed.

All these analyses will be based on the most updated MedDRA version available prior to the database lock.

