5.1.1.2 Adverse event start date imputation

The following table explains the notation used in the logic matrix. Please note that **missing start dates** will not be imputed.

	Day	Month	Year
Partial Adverse Event Start Date	Not used	MON	YYYY
Treatment Start Date	Not used	TRTM	TRTY

The following matrix explains the logic behind the imputation.

	MON MISSING	MON < TRTM	MON = TRTM	MON > TRTM
YYYY MISSING	(1) No convention	(1) No convention	(1) No convention	(1) No convention
YYYY < TRTY	(2.a) Before Treatment Start	(2.c) Before Treatment Start	(2.c) Before Treatment Start	(2.c) Before Treatment Start
YYYY = TRTY	(4.a) Uncertain	(4.c) Before Treatment Start	(4.d) Uncertain	(4.d) After Treatment Start
YYYY > TRTY	(3.a) After Treatment Start	(3.c) After Treatment Start	(3.c) After Treatment Start	(3.c) After Treatment Start

Before imputing AE start date, find the AE start reference date.

1. If the (imputed) AE end date is complete and the (imputed) AE end date < treatment start date then AE start reference date = min (informed consent date, earliest visit date).
2. Else AE start reference date = treatment start date

Impute AE start date -

1. If the AE start date year value is missing, the date uncertainty is too high to impute a rational date. Therefore, if the AE year value is missing, the imputed AE start date is set to NULL.
2. If the AE start date year value is less than the treatment start date year value, the AE started before treatment. Therefore:
 - a. If AE day and month are missing, the imputed AE start date is set to the mid-year point (01JulYYYY).
 - b. If AE month is missing but day is not missing, the observed start date will be used with month imputed as JulYYYY.
 - c. Else if AE month is not missing, the imputed AE start date is set to the mid-month point (15MONYYYY).
3. If the AE start date year value is greater than the treatment start date year value, the AE started after treatment. Therefore:
 - a. If the AE day and month are missing, the imputed AE start date is set to the year start point (01JanYYYY).
 - b. If AE month is missing but day is not missing, the observed start date will be used with month imputed as JulYYYY.
 - c. Else if the AE month is not missing, the imputed AE start date is set to the later of (month start point (01MONYYYY), AE start reference date + 1 day).
4. If the AE start date year value is equal to the treatment start date year value:

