5.1.2.2 Concomitant treatment start date imputation

The following table explains the notation used in the logic matrix. Please note that **missing start dates** will not be imputed.

	Day	Month	Year
Partial CMD Start Date	Not used	MON	YYYY
Treatment Start Date	Not used	TRTM	TRTY

The following matrix explains the logic behind the imputation.

	MON MISSING	MON < TRTM	MON = TRTM	MON > TRTM
YYYY MISSING	(1) Uncertain	(1) Uncertain	(1) Uncertain	(1) Uncertain
YYYY < TRTY	(2.a) Before Treatment Start	(2.c) Before Treatment Start	(2.c) Before Treatment Start	(2.c) Before Treatment Start
YYYY = TRTY	(4.a) Uncertain	(4.b) Before Treatment Start	(4.a) Uncertain	(4.c) After Treatment Start

YYYY > TRTY	(3.a) After Treatment Start	(3.c) After Treatment Start	(3.c) After Treatment Start	(3.c) After Treatment Start
-------------	----------------------------------	----------------------------------	----------------------------------	----------------------------------

1. If the CM start date year value is missing, the imputed CM start date is set to one day prior to treatment start date.
2. If the CM start date year value is less than the treatment start date year value, the CM started before treatment. Therefore:
 - a. If the CM day and month are missing, the imputed CM start date is set to the mid-year point (01JulYYYY).
 - b. If CM month is missing but day is not missing, the observed start date will be used with month imputed as JulYYYY.
 - c. Else if the CM month is not missing, the imputed CM start date is set to the mid-month point (15MONYYYY).
3. If the CM start date year value is greater than the treatment start date year value, the CM started after treatment. Therefore:
 - a. If the CM day and month are missing, the imputed CM start date is set to the year start point (01JanYYYY).
 - b. If CM month is missing but day is not missing, the observed start date will be used with month imputed as JanYYYY.
 - c. Else if the CM month is not missing, the imputed CM start date is set to the month start point (01MONYYYY).
4. If the CM start date year value is equal to the treatment start date year value:
 - a. And the CM day and CM month are missing or the CM day is missing and CM month is equal to the treatment start date month, then the imputed CM start date is set to one day prior treatment start date.
 - b. Else if the CM month is less than the treatment start date month, the imputed CM start date is set to the mid-month point (15MONYYYY).

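### AE start-date rule 3.b imputes July in the year after treatment start, outside the on-treatment window, so an event with no end date drops out of the TEAE tables

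*SAP*

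**What the plan says.** SAP 5.1.1.2 sorts partial AE start dates by comparing the event year with the treatment start year. For a later year it states: "If the AE start date year value is greater than the treatment start date year value, the AE started after treatment". Three sub-rules follow.

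- **3.a**, day and month both missing: "the imputed AE start date is set to the year start point (01JanYYYY".
- **3.b**, day known, month missing: "If AE month is missing but day is not missing, the observed start date will be used with month imputed as JulYYYY". Rule 2.b, for years before treatment, uses the same wording.
- **3.c**, month known: the later of the first of that month and the day after the AE start reference date.

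The logic matrix above the rules marks the day as not used. It sends every month-missing record in the later-year row to 3.a.

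The concomitant-medication rules in SAP 5.1.2.2 have the same structure, but their rule 3.b reads: "If CM month is missing but day is not missing, the observed start date will be used with month imputed as JanYYYY".

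For counting, SAP 2.8.1 says: "Summary tables for AEs and SAEs will summarize only on-treatment events, with a start date during the on-treatment period". SAP 2.1.1.5 defines that period: "The on-treatment period lasts from the date of first administration of study treatment to 30 days after the date of the last actual administration". Protocol 6.1.4 says: "The planned treatment duration is three months", and Protocol Table 8-1 puts the final visit on Day 90.

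Only one later step can change an imputed AE start date. If a complete or imputed end date exists and is earlier than the imputed start, the start is moved to the end date. Under SAP 5.1.1.1, an ongoing event or one with a missing end year receives no imputed end date.

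**The concern.** Rule 3 recognises these events as having started after treatment began, yet sub-rule 3.b gives them a date that the TEAE definition cannot accept under the planned schedule. Knowing the day as well as the year should not make the imputation worse, but here it moves the event from 1 January (3.a) to July.

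The rule also breaks the pattern around it. July suits branch 2, where 2.a uses the mid-year point. In branch 3 the companion rule uses the start of the year. The other rules for events in or after the treatment-start month place the event early: 3.c and 4.d at the start of the month or just after the reference date, 4.a at the reference date plus one day, and 4.b in the reference month.

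The frequency of TEAEs and TESAEs is the secondary safety endpoint, so the tables affected are those that report it. No efficacy analysis is touched.

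**Working it through.** The plan gives no figure on this point to reproduce. The check is a calendar calculation.

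**Inputs.** Planned exposure is 90 days (Protocol 6.1.4 and Table 8-1). The window ends 30 days after last dose (SAP 2.1.1.5). Call the treatment start year Y. Rule 3.b then gives a date from 1 to 31 July of Y+1.

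**Latest possible window end.** Window end = first dose + (exposure − 1) + 30 days. The latest first dose in year Y is 31 December.

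- Y+1 not a leap year: 31 December + 89 days = 30 March; + 30 days = 29 April.
- Y+1 a leap year: 29 March; + 30 days = 28 April.

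The earliest date under 3.b is 1 July, which is 63 days after 29 April or 64 days after 28 April.

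**All start dates.** At 90 days of exposure, the window reaches Y+1 for first doses from 4 September to 31 December, which is 119 dates. With 31 possible days of the month there are 119 × 31 = 3689 combinations.

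| Month imputed in 3.b | Inside the on-treatment window |
|---|---|
| July (as written) | 0 of 3689 |
| January (as in CM rule 3.b) | 3224 of 3689 (87%) |

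The 465 January dates outside the window belong to subjects whose window closes during January. For them, the same day in any later month is outside too. January therefore counts an event whenever at least one possible month would place it in the window. These are counts of date combinations, not an estimate of how many events are affected.

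**Longer exposure.** The window runs from the actual last dose, so overruns matter. July stays at zero for assumed exposures of 92, 100, 120 and 150 days. For 1 July to fall inside the window, the last dose must be on or after 1 June of Y+1. After a 31 December start that is 153 days of exposure (154 if Y+1 is a leap year), about 63 days beyond plan.

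**Example (illustrative dates, Y+1 not a leap year).** First dose 15 November, last dose 12 February, window closes 14 March. An ongoing event is recorded as day 10, month unknown, of the second year. Rule 3.b dates it 10 July, so it is not a TEAE, although 10 January, 10 February and 10 March are all in the window. There is no end date, so the closing rule does not apply. If the event had ended on 1 March, its start would be moved to 1 March and it would count.

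**The case against.** A reader might infer that every event reaching this branch is always lost from the safety report. The documents do not support that, for these reasons.

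- **The matrix conflicts with the list.** Read literally, the matrix sends month-missing records in this row to 3.a, which is 1 January. A programmer who followed it would avoid the problem. However, 2.b and 4.b have no matrix cell either, so the matrix may simply be abbreviated. This makes the SAP inconsistent; it does not make 3.b right.
- **The detailed algorithm is elsewhere.** SAP 5.1 calls these rules the general approach and defers detail to the programming specifications, which are not available here. That stands as a limit on certainty, but a specification faithful to 3.b would code July.
- **The events are not lost altogether.** SAP 2.8.1 keeps other AEs and SAEs in listings. The tables count subjects, so a subject with another TEAE still appears in the overall row, and in the system-organ-class row if the other event is in the same class.
- **The window depends on actual dosing.** The exclusion holds up to about 152 days of exposure, not without limit.
- **The branch may be empty.** It needs a known day and year, a missing month, a start year after the treatment start year, and no usable end date. The documents give no enrolment dates. AEs are sought at each visit and missing values are queried (Protocol 10.1.1 and 11.2). SAEs are reported within 24 hours and their documentation is fully verified (Protocol 10.1.3 and 11.3), so an SAE is especially unlikely to arrive in this form.

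All of this limits the size of the problem. None of it gives a reason for July.

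**Conclusion.** Rule 3.b is wrong as written, at low severity. It conflicts with rule 3.a, with the matrix and with the concomitant-medication rule. For treatment as planned, and for exposure up to about 152 days, it puts the event outside the on-treatment period. An event with no complete or imputable end date then leaves the TEAE and TESAE summary tables and is only listed. Compared with January, the error can only lower the counts.

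The conclusion assumes that the written sub-rule prevails over the matrix, and that end dates are imputed before start dates, as the start-date rules imply by using the imputed end date. The number of affected records cannot be derived from the documents and is probably very small or nil. Nothing here suggests a material distortion of the safety results.

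**What to change.** In SAP 5.1.1.2, AE rule 3.b, change JulYYYY to JanYYYY. That agrees with AE rule 3.a and with concomitant-medication rule 3.b. State in the matrix that month-missing records with a known day follow 3.b, so that matrix and list no longer compete.

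The later-of wording in rule 3.c need not be added. The reference date is at latest the treatment start date, in the earlier year, so that date plus one day is at most 1 January of the event year and the January date is always returned.

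The cost is one word in the SAP, a note to the matrix and a matching line in the programming specification. It is best done before database lock, so that no event is reclassified after unmasking.

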 - a. And the AE day and month are missing the imputed AE start date is set to the AE reference start date + 1 day.

- b. If AE month is missing and day is not missing, the observed start date will be used with month imputed as the reference start month.
- c. Else if the AE month is less than the treatment start month, the imputed AE start date is set to the mid-month point (15MONYYYY).
- d. Else if the AE month is equal to the treatment start date month or greater than the treatment start date month, the imputed AE start date is set to the later of (month start point (01MONYYYY), AE start reference date + 1 day).

If complete (imputed) AE end date is available and the imputed AE start date is greater than the (imputed) AE end date, then imputed AE start date should be set to the (imputed) AE end date.

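### AE start-date rule 4.b (same year, month missing, day known) has no floor at first dose, so a few on-treatment events could be dated before treatment and leave the TEAE tables

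*SAP*

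**What the plan says.** SAP 5.1.1.2 first sets a reference date. If a complete (imputed) end date precedes treatment, the reference is the earlier of consent and first visit. In all other cases: "Else AE start reference date = treatment start date".

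Three rules for events starting in the treatment-start year matter here:

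- **4.a**, day and month both missing: "the imputed AE start date is set to the AE reference start date + 1 day".
- **4.b**, month missing and day known: "the observed start date will be used with month imputed as the reference start month".
- **4.d**, month known and equal to or after the treatment-start month: "the imputed AE start date is set to the later of (month start point (01MONYYYY), AE start reference date + 1 day".

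A closing check applies if the imputed start is later than a complete (imputed) end date: "then imputed AE start date should be set to the (imputed) AE end date".

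The rules are preceded by a grid introduced with the words "The following matrix explains the logic behind the imputation". For same year and month missing it shows only 4.a, labelled Uncertain. In the notation table, the row "Partial Adverse Event Start Date" marks Day as not used. Rules 2.b, 3.b and 4.b appear nowhere in the grid.

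Under SAP 2.8.1, AE and SAE tables include only events that start in the on-treatment period. SAP 2.1.1.5 defines it: "The on-treatment period lasts from the date of first administration of study treatment to 30 days after" the last dose. Other events are only listed.

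**The concern.** Rules 4.a and 4.d settle an uncertain same-year onset at one day after the reference date or later. The event therefore counts as treatment-emergent unless its end date shows otherwise. Rule 4.b does not do this. It fixes the month as that of first dose and never compares the result with first dose. The closing check cannot repair this, because it only moves a start earlier.

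The result is odd: a more complete record can be classified less conservatively. With day and month both unknown, an event is counted. Once the site supplies the day, the same event may be lost. Rule 4.b can also form a date that does not exist, such as 31 February, and no printed rule deals with that.

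At stake is the secondary safety endpoint, the frequency of TEAEs and TESAEs.

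**Working it through.** The plan states no figure on this point, so there is none to reproduce. The check applies the printed rules to dates.

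**Formula.** Let first dose be day d of month m in year y, and let the recorded AE day be k with year y. If the event did not end before first dose, the reference date is first dose, and rule 4.b gives start = (k, m, y). The start precedes first dose whenever k < d.

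**Example.** First dose 20 March; true onset 10 April; recorded as day 10, month unknown, same year; event ends in May.

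- 4.b: 10 March, before first dose, so not a TEAE.
- 4.a, had the day also been missing: 20 March + 1 day = 21 March, a TEAE.
- 4.d, had the month been recorded: March gives the later of 1 and 21 March = 21 March; April gives the later of 1 April and 21 March = 1 April. Both are TEAEs.
- Closing check on the 4.b result: 10 March is not after an end date in May, so nothing changes.

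**Enumeration.** Inputs from the documents: 90 days of treatment plus 30 days, so onsets on days 0 to 119. Assumptions: first-dose dates uniform over a non-leap year; onset in the same calendar year; day known and month missing. This gives 36,660 pairs of first-dose and onset dates.

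| Onset pattern | Dated before first dose by 4.b |
|---|---|
| Uniform, days 0–119 | 16,553 / 36,660 = 45.2% |
| Uniform, days 0–29 | 4,728 / 10,515 = 45.0% |
| Uniform, days 0–14 | 1,155 / 5,370 = 21.5% |
| Exponential, mean 7 / 15 / 30 / 60 days | 18.7 / 30.6 / 37.8 / 41.6% |

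A further 430 / 36,660 = 1.2% form a date that does not exist. For December first doses the share is 0 of 496, because later onsets in the same year are in the same month. The share also depends strongly on the day of first dose. With first doses in January to August it is 0% for the 1st, 45% for the 15th, 62% for the 20th and 89% for the 28th.

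**The proposed clause (see fix), same 36,660 pairs.** Run with no end date and with end dates 0, 7 and 30 days after onset: 0 dated before first dose, and none dated later than the true onset.

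**Cost of the clause.** Take true onsets 1 to 7 days before first dose, in the same year and not ended before first dose: 2,527 pairs. The number dated on or after first dose, and so wrongly counted as TEAEs, is:

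- Rule 4.b now: 262 / 2,527 = 10.4% (46 more form an invalid date).
- With the clause, event ongoing: 2,338 / 2,527 = 92.5%.
- With the clause, event ended 0, 7 or 14 days after first dose: 262, unchanged.
- Ended on day 21: 283 / 2,527 = 11.2%. Ended on day 28: 1,822 / 2,527 = 72.1%.
- December first doses: 189 of 217 are correctly pre-dose now, and all 189 stay so.

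**The case against.** **The matrix.** A reader might infer that SAP 5.1.1.2 contains two rival rules, one in the grid and one in the text, that give the same record different TEAE status. The documents do not support that. By its own words 4.a needs both day and month to be missing, so a record with a known day fails it and meets 4.b. The grid ignores day and leaves out every b-rule. It is an incomplete summary, and its label Uncertain suits 4.b, which can fall either side of first dose. What stands is that the grid should be completed.

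**Deferred detail.** SAP 5.1 calls its rules a general approach and leaves the detailed algorithms to programming specifications, which are not among the documents. Those may already contain a floor or invalid-date handling. But 4.b is a stated rule with a stated result, not a gap, and followed exactly it misdates events.

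**Possibly no records.** AEs are sought at every visit (Protocol 10.1.1) and missing values are queried (Protocol 11.2). Nothing shows that the eCRF accepts a date with day and year but no month. For SAEs, reporting within 24 hours of awareness (Protocol 10.1.3) makes the pattern remote. All of this stands, and it keeps the point minor.

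**A trade-off.** The clause counts more pre-dose events as TEAEs, as shown above. That also stands, but it is the direction 4.a and 4.d already take for uncertain same-year onsets.

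**A neighbouring rule.** Rule 3.b places next-year events of this pattern in July. With no end date, all 7,140 next-year on-treatment onsets in a matching enumeration then fall beyond day 119. That is a separate rule, which the change to 4.b does not touch.

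**Conclusion.** The point holds as a minor defect in a stated rule. Rule 4.b lacks the floor that 4.a and 4.d have. Applied as printed, it dates some on-treatment events before first dose and removes them from the TEAE or TESAE tables.

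Within this date pattern the share is about 19% to 45%, plus about 1% with impossible dates (uniform onset over days 0 to 119). It rests on assumed onset patterns and evenly spread first-dose dates. It should not be read as a share of all adverse events: the number of such records is unknown and may be zero.

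The practical effect is small. The tables are descriptive, the same rule applies to both arms, and the event stays in the listings. A table row changes only if the subject has no other qualifying event in that row. Efficacy is not affected.

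**What to change.** Add to rule 4.b: if the date formed is before the AE start reference date, or is not a valid calendar date, use the earliest valid date on or after the reference date that has the observed day, provided it lies in the recorded year and is not after the (imputed) AE end date. Otherwise use the latest valid date before the reference date that has that day.

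In the example the start becomes 10 April, which keeps the recorded day. Events known to have ended before first dose stay pre-treatment, because the start is held no later than the end date.

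In the matrix, change the cell for same year and month missing to 4.a if day missing, 4.b if day known.

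A plain floor at reference date + 1 day would be shorter and would also leave no valid formed date before first dose. But it discards the recorded day, and it would move all 189 correctly dated December pre-dose cases to after first dose.

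The change costs one clause, one matrix cell and the matching line in the programming specification, best settled before unmasking. No new data are needed. The price is the one quantified above: pre-dose events of this pattern that are ongoing, or end about four weeks or more after first dose, would mostly be counted as TEAEs.
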